In the past, recording of ventricular fluid pressure has proved to be a reliable method in clinical neurosurgery, as shown by Lundberg et al.¹⁸⁻²⁰ Furthermore, some authors recorded supratentorial pressure during posterior fossa surgery with the intention of obtaining continuous information on the pressure state in major intracranial compartment.^{3, 21, 22}

Of note, some surgeons were reluctant to introduce direct subdural posterior fossa monitors for a number of reasons. Some of the possible problems may include cerebrospinal fluid (CSF) leaks, cranial nerve dysfunction, and the possibility of brainstem irritation with resulting autonomic dysfunction. Yet, many recent studies have showed the safety and feasibility of intracranial monitoring in the posterior fossa.^{1, 21, 23-26}

PRESENT

With regards to pathophysiology and clinical practice, the intracranial pressure (ICP) profiles in the supratentorial and infratentorial compartments remain unclear. After a neurosurgical operation in the posterior fossa there are most likely pressure differences between supra- and infratentorial spaces.²⁷ It is well known that the pressure within the skull is unevenly distributed, with demonstrated ICP gradients.²⁵ By contrast, Rieger et al²³ reported no significant differences between supratentorial and infratentorial ICP values in an animal model. The infratentorial ICP elevation in the presented pig model led to a uniform ICP elevation in the intracranial space without development of a considerable pressure gradient below and above the tentorium. Importantly, in the low pressure part of the ICP curve, cerebrospinal fluid connects the compartments and contributes to the pressure equilibrium.

To rely on autonomic changes or neurological deterioration as signs of a postoperative complication narrows the temporal margin of safety for the institution of treatment.

It has been the policy of our Department to electively monitor all complex posterior fossa procedures via a supratentorial intracranial multimodal monitoring; however, it remains unclear whether an acute change in the posterior fossa would be reflected by the supratentorial monitor prior to clinical deterioration.

Thus, we intend to apply the intracranial multimodal monitoring in both infratentorial and supratentorial compartments simultaneously. Such coincident measurements most likely will be the most sensitive way to assess focal swelling, ischemia and tissue perfusion in the posterior fossa structures.

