- 4) facilitate the neurointensive care of these patients including ventilatory support, the use of positive end-expiratory pressures, continued osmotherapy, and patient positioning; ultimately
- 5) better understand of pathophysiological processes with
- 6) immediately identify of complications with subsequent prompt intervention if needed.

QUESTIONS

- * Is infratentorial multimodal neuromonitoring safe and feasible, and necessary?
- * Do data assessed by multimodal monitoring in the posterior fossa correlate with data from the supratentorial compartment?
- * Is infratentorial multimodal neuromonitoring able to timely predict complications such as local swelling, mass effect, vasospasm, ischemia, or infarction?
- * Is infratentorial multimodal neuromonitoring of value in daily clinical practice?

HYPOTHESES

- The intracranial multimodal monitoring in the posterior fossa is safe and feasible, without any increased risk due to additional probes.
- Data generated by infratentorial multimodal neuromonitoring do not completely correlate with data from standardized supratentorial multimodal neuromonitoring. There are significant differences in ICP- or brain tissue oxygenation values between the supratentorial and infratentorial compartments.
- The infratentorial multimodal monitoring immediately detects all relevant complications related to posterior fossa lesions including mass effect, local swelling, postoperative hematoma, ischemic events, decrease in the blood flow, vasospasm and inadvertent or prolonged vessel occlusion, or infarction, resulting in prompt therapeutic intervention if necessary.
- Additional information from infratentorial probes facilitate to maintain the critical patients including ventilatory support, the use of positive end-expiratory pressures, continued osmotherapy, and patient positioning.

CLINICAL RELEVANCE

Our prospective study can provide better guidance and optimization of clinical therapy through a comprehensive assessment of patients harboring posterior fossa lesions.

This study has very high potential to generate a new intellectual property, to yield discoveries improving the prediction of complications and monitoring the effects of treatments. The data will offer better understanding of pathophysiological mechanisms in posterior fossa lesions.

STUDY DESIGN

METHODS

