In phase I of the study 15 patients with posterior fossa lesions who require prolonged neurointensive care and in which any intracranial invasive intervention is indicated regardless of used technique or treatment modality will be enrolled in the study. The indication for posterior fossa lesion treatment will be decided on a case-by-case basis by our neurosurgical team irrespective of the study.

The study will start as a monocentric clinical trial (pilot study), and subsequently in phase II the study is planned to be continued as a multicentric trial.

In the majority of patients, ICP- and LICOX sensors are usually placed in the right frontal lobe and/or at the site of the lesion. In case of posterior fossa surgery, additional probes (ICP / LICOX) will be placed into the surgical field.

The neuromonitoring data will be recorded and analyzed. Additionally, demographic data, all treatment-related complications, and management of intracranial hypertension will be recorded.

All adverse effects will be noted and reported, even if no clinical consequence will ensue. Non-neurological complications such as cardiopulmonary complications will be documented separately.

After the invasive treatment of the posterior fossa lesion, all patients will undergo CT and/or MRI as standard of care within 72 hours after the intervention (the acute phase) as a protocol for detection of procedure-related complications. As standard of care, an additional follow-up MRI will be performed if needed. In stable patients a preoperative MRI will also be performed before invasive treatment

The following outcomes will be evaluated and analyzed: mean ICP, ICP pulse amplitude, respiratory waves, slow waves and the RAP (compensatory reserve) index of supra- and infratentorial ICP signals, transtentorial difference, brain tissue oxygenation, blood saturation, ASTRUP, and further vital parameters, peri- and postoperative morbidity and mortality, procedure-related morbidity including infection, hematomas, epilepsy, cerebral puncture, cranial nerve palsies, and CSF leaks, perioperative cerebral ischemia, long-term neurological morbidity and mortality, and overall neurological outcome.

Institutional review board will be obtained by the Ethics Committee of the Medical University Innsbruck, Austria. Informed consent will be acquired from all patients for participation in the study during the study period according to local requirements.

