Informed consent will be acquired from all patients for participation in the study during the study period.

All interventions and neuroimaging (e.g. MRI) will be performed as a part of routine clinical care and no modifications will be introduced in the treatment or the follow-up modalities currently used by the Department of Neurosurgery / Neuroradiology, except ^{31}P -MRS (see above).

CALCULATION OF THE NUMBER OF CASES

The study is designed as a prospective clinical trial (the sample of 30 patients was selected according to epidemiologic data and estimated annual incidence of posterior fossa lesions in Central Europe).

Regarding the complex patient cohort a high drop-out rate for MRI in the acute phase due to unstable patients with a consecutive infeasibility of MRI is to be expected.

ANALYSIS

Data collection

Clinical and procedural data will be collected prospectively. The adverse events are classified in three groups, according to their mechanism:

- * Lesion-related events
- * Intraoperative / intraprocedural (iatrogenic) events
- * Device-related problems

The outcome of adverse events is classified in four groups:

- * No clinical modification
- * Transient deficit(s)
- * Permanent deficit(s) (deficit(s) remaining at the 6-months follow-up)
- * Death

All-cause morbidity is defined as a modified Rankin score ≥ 3 . When the preoperative mRS was greater than 2, the all-cause morbidity is defined as any increase in the mRS value.

STATISTICAL ANALYSIS

The distribution of continuous variables will be described by using means and standard deviations, and discrete variables will be described as frequencies, percentages, and confidence intervals. The Clopper-Pearson exact method will be used to construct 95% confidence intervals (CIs).

The characteristics of both treatment groups will be compared by using Chi² test. All outcome results will be compared between the study groups by using a MannWhitneyU test, or Student t test where appropriate. P <0.05 is considered indicative of a statistically significant difference.

LITERATURE - REFERENCES

1. Mizunari T. [Clinical aspects and intracranial pressure monitoring in cases of traumatic posterior fossa hematoma]. *Nihon Ika Daigaku zasshi* 1990;57:334-343
2. Schroder R. [Expansive processes in the posterior cranial fossa and changes in intracranial pressure during the preoperative and postoperative period]. *Ceskoslovenska neurologie a neurochirurgie* 1982;45:306-314

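### All outcomes are tested at P<0.05 with no primary comparison or multiplicity control, and hypothesis 2 can be met by either of two measures: nominal error up to 9.75%, actual rate not fixed by the plan

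*Combined protocol and SAP*

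**What the plan says.** The protocol and SAP are one document. Four places matter.

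- **Hypotheses, second item:** after stating that infra- and supratentorial data do not correlate completely, it says "There are significant differences in ICP- or brain tissue oxygenation values between the supratentorial and infratentorial compartments".
- **Study Design, Methods:** the outcomes form one unranked list. It includes "mean ICP, ICP pulse amplitude, respiratory waves, slow waves and the RAP (compensatory reserve) index of supra- and infratentorial ICP signals, transtentorial difference", followed by brain tissue oxygenation, other physiological measures, morbidity and mortality.
- **Statistical Analysis:** "All outcome results will be compared between the study groups by using a MannWhitneyU test, or Student t test where appropriate". The threshold follows: P<0.05 "is considered indicative of a statistically significant difference". Sidedness is not stated.
- **History (Present):** "we intend to apply the intracranial multimodal monitoring in both infratentorial and supratentorial compartments simultaneously". The two compartments are therefore measured in the same patients.

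No section names a primary outcome or comparison, an order of testing, or an adjustment for multiple tests. The unit of analysis (one value per patient or repeated readings) is not stated either.

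**The concern.** A 5% threshold limits false positives for one pre-specified test. Here it applies to every outcome, and hypothesis 2 joins two measures with an *or*. If ICP and oxygenation are each tested at 0.05 and either may carry the claim, there are two chances of a false finding. The Methods list offers further supra/infra signals on an equal footing, so a report could lead with whichever crossed the line.

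This matters because the text is not purely descriptive. The Aims section sets out to prove safety and feasibility and to establish the method as standard of care, hypothesis 2 is phrased in terms of significance, and a multicentre phase II is to follow. A chance difference reported as confirming hypothesis 2 would feed into that next step.

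**Working it through.** **Plan's own figure.** The plan gives only a per-comparison threshold of 0.05. It states no family-wise rate, so there is none to reproduce.

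**Inputs**

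- Threshold per test: 0.05 (Statistical Analysis); two-sided assumed.
- Tests that can support hypothesis 2: 2, ICP and brain tissue oxygenation (Hypotheses).
- Supra/infra signal outcomes: 6 (Methods), namely mean ICP, pulse amplitude, respiratory waves, slow waves, RAP index and tissue oxygenation. The count is a reading of the list; taking the transtentorial difference as a separate outcome makes it 7.
- Patients: 15 in phase I (Methods). The section on the number of cases gives 30. The nominal rates below do not depend on which applies.
- Correlations: none in the documents; a range is assumed.

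**Step 1. Independent tests of true 5% size.** The chance of at least one false significant result is 1 − (1 − 0.05)^k.

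- k = 2: 1 − 0.95² = 0.0975, or 9.75%.
- k = 6: 1 − 0.95⁶ = 0.265, or 26.5%.
- k = 7: 1 − 0.95⁷ = 0.302, or 30.2%.

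Under any dependence the bound is k × 0.05: 10% for two tests and 30% for six.

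**Step 2. Correlated outcomes, valid paired tests.** These are simulated two-sided one-sample t tests on within-patient differences, n = 15, with equal correlation between outcomes.

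| Tests | correlation 0.3 | correlation 0.8 |
|---|---|---|
| 2 | 9.6% | 8.0% |
| 6 | 24.7% | 14.8% |

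A second simulation on normal test statistics gave 9.5% and 7.9% for two tests, and 24.1% and 13.9% for six. For six correlated outcomes the range is therefore about 14% to 25%.

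**Step 3. The tests the plan names.** Mann-Whitney is an unpaired test, and a Student t test between groups is most naturally read as unpaired too. With one value per patient per compartment, n = 15 and no true difference, the unpaired t test simulates as follows. The last two columns are 1 − (1 − p)² and 1 − (1 − p)⁶.

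| Assumed within-patient supra/infra correlation | Per test, p | Two tests | Six tests |
|---|---|---|---|
| 0 | 5.0% | 9.8% | 27% |
| 0.3 | 2.1% | 4.1% | 12% |
| 0.5 | 0.85% | 1.7% | 5% |
| 0.7 | 0.12% | 0.2% | 0.7% |

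Simulation error moves the two-test figures by a tenth or two of a percentage point. Mann-Whitney and n = 30 give similar results. A paired t test stays at about 5% per test throughout.

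**Step 4. After the fix.** One pre-specified test at 0.05 has 5% error. Holm on two tests requires the smaller P-value to be below 0.05/2 = 0.025. If neither difference is real and the tests are independent, the error is 1 − 0.975² = 4.9%.

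**The case against.** The strongest counter-argument is that the percentages are not the error rate of this plan. The named tests are most naturally unpaired while the data are paired, and Step 3 shows that the rate for two tests could then lie below 5%. That stands. A reader might infer that the real false-positive rate is about 10%, or two to five times the threshold; the documents do not support this. They give neither the within-patient correlation nor the unit of analysis, and pooling repeated readings as independent could push the rate the other way. The low rate under unpaired testing is also no safeguard: it comes from a test that ignores the pairing, and it costs power.

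Second, a reader might attach the 26.5% to hypothesis 2. That hypothesis names only ICP or oxygenation values, so by this count two tests apply. The six-outcome figure describes the Methods list, and five of those six signals derive from ICP recordings, so independence is a poor default.

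Third, the plan never says that a single P<0.05 confirms hypothesis 2, and it promises no family-wise 5% that it then breaches. The groups to be compared are not defined in what is a single cohort. This stands too: the *either one suffices* rule follows from the wording but is not stated.

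Fourth, this is a 15-patient pilot whose first aim is safety and feasibility. That lowers the stakes, but it does not turn a section that tests every outcome for significance into a descriptive one.

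**Conclusion.** The point holds in limited form. The plan tests all outcomes at P<0.05 with no primary comparison and no multiplicity control, and the wording of hypothesis 2 lets either of two measures support it.

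The nominal cost is up to 9.75% for hypothesis 2. It is 26.5% across six signal outcomes if they are independent, and less under the positive correlations examined. Both figures rest on each test having a true 5% size. The correlations are assumed, and the count of six is a reading of the Methods list.

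The rate under the plan as written cannot be stated and could be lower or higher. What can be said is that 0.05 is not a controlled error rate for hypothesis 2. Correcting the pairing without settling the multiplicity would bring the nominal figures into play, so the two should be dealt with together. For a pilot this is a cheap and worthwhile improvement rather than a flaw that undermines the study.

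**What to change.** In Statistical Analysis:

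1. Name one primary comparison for hypothesis 2: the within-patient transtentorial difference in mean ICP, as one value per patient over the monitoring period. Test it at two-sided 0.05 with a paired t test or Wilcoxon signed-rank test in place of an unpaired test.
2. If brain tissue oxygenation may also support hypothesis 2, test it as a within-patient difference too, and apply Holm across the two.
3. Label the remaining outcome comparisons exploratory and report them with 95% confidence intervals.

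In Hypotheses, align the *or* wording of the second item with whichever option is chosen.

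The cost is a few sentences, with no change to patients, data collection or sample size. The safety and feasibility aim is untouched, since the primary comparison is named only for hypothesis 2. The small downside is that fewer results can be called confirmed.
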